7.1.2 Treatment Period (Days 1 to 5)

Study Site Visits (Days 1, 3, and 5):

Subjects who meet all inclusion criteria and none of the exclusion criteria to the satisfaction of the Investigator will be eligible to enter the study and will be randomized 1:1 to receive 800 mg of EDP-938 or placebo. Subject randomization will be stratified by the presence or absence of asthma/COPD.

Eligible subjects must complete the Day 1 biological sample collections (ie, blood, urine, and nasopharyngeal swab[s]) prior to receiving the first dose of EDP-938 or placebo. Day 1 blood

and urine samples will be sent to both local (expedited testing and reporting) and central laboratories. Nasopharyngeal swab(s) will be sent to the central laboratory only.

Eligible subjects will receive an electronic data capture handheld device (ERT[®] electronic clinical outcome assessment [eCOA] Handheld eDiary) to use for the duration of the study.

[REDACTED]

The device will also serve to alert the subject when it is time for study drug dosing. The subject will receive instruction on the proper use and care of the device, including the recording of the first dose, and the device should be brought to each study site visit. In case the subject is unable to complete any assessments or recordings into the device for technical reasons, the subject will also be provided with a paper diary(ies) as a back-up.

The subject will be instructed on the use of concomitant medications during the study, including the use of acetaminophen as the study-specific analgesic/antipyretic (see [Section 5.8](#) and [Section 5.9](#)).

Subjects will receive the first dose of study drug while at the study site. After the first dose, subjects will be instructed to take 800 mg of EDP-938 or placebo once daily at approximately the same time every day (± 1 hour) on each of the 4 subsequent days. The subject will also receive instruction on the appropriate storage and transport of study drug (see [Section 5.3](#)).

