8.3.8 Respiratory Syncytial Virus Symptom Diary

At Screening and at timepoints indicated in the SoA ([Appendix 1](#)), subjects will assess the severity of RSV-related signs and symptoms and self-complete the 13-point RSV symptom diary. The 13-item diary will consist of grading symptoms on a scale of 0 to 3, where Grade 0 is absence, Grade 1 is just noticeable, Grade 2 is bothersome but does not prevent participation in activities, and Grade 3 is bothersome and interferes with activities. The 13 RSV symptoms assessed will comprise nasal discharge, nasal congestion, malaise/tiredness, headache, sinus congestion, sneezing, sore throat, hoarseness, cough, shortness of breath, respiratory wheeze, earache, and/or symptoms of fever. The RSV symptom diary will be completed twice daily at the same times each day ± 2 hours as an eCOA. In case the subject is unable to complete the RSV symptom diary assessment for technical reasons, the subject will also be provided with a paper diary(ies) as a back-up. If a subject plans to take acetaminophen within 2 hours of the scheduled RSV symptom diary completion, then the RSV symptom diary should be completed immediately before the subject takes acetaminophen or 4 hours after taking acetaminophen.

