8.4 Laboratory and Diagnostic Procedures

At Screening, the rapid viral diagnostic screen will be performed on site. Subsequent virology assessments will be sent to the central laboratory(ies).

On Day 1, enrolled subjects will undergo the clinical laboratory evaluations of blood and urine samples specified [Table 2](#), which will be performed at the local site laboratory (expedited testing and reporting) and the central laboratory(ies). Subsequent clinical laboratory evaluations will be performed by the central laboratory(ies).

The Day 1 collection of blood, urine, and nasopharyngeal swab samples will be completed prior to administration of study drug.

A Laboratory Manual will be provided to the site detailing kit contents, reordering supplies, sample collection, handling, storage, and shipment instructions. All unblinded laboratory values will be reviewed by the Investigator, documented, and the results maintained in the source documents. All out-of-range laboratory findings require an interpretation as to whether or not they are of clinical significance. Clinically significant laboratory findings in the opinion of the Investigator should be recorded as an AE (or SAE as appropriate) (see [Section 9.1](#)).

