11.6 Efficacy Analyses

11.6.1 Primary Efficacy Analyses

The primary efficacy analysis will be performed on the TSS AUC. The TSS AUC is measured twice daily (before or after treatment, morning/evening) using the 13-point symptom scale. Date and time of completion and symptom severity (graded 0 to 3) will be recorded. The TSS will be derived for each from the last nonmissing measurement (Baseline) collected prior to dosing to the final on Day 14. The average daily TSS will be computed as part of the primary efficacy endpoint. The AUC will be calculated using the trapezoid rule (*Matthews et al., 1990*). The TSS will be compared between EDP-938 and placebo using an analysis of covariance (ANCOVA) model with treatment group and stratification factor as fixed effects and the baseline TSS as a covariate. Treatment groups will be compared using a type III sum-of-squares. The least-squares means and two-sided 95% confidence intervals (CI) will be presented for individual groups and

the difference between groups. Descriptive statistics will include at a minimum the number of nonmissing measurements, mean, median, minimum, maximum, and 95% CI for the mean.

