14. APPENDICES

Appendix 1: Schedule of Assessments

Period Day	Screening	Treatment					Follow-up			
	1 Screening	1 Eligible Subjects ^a	2	3	4	5 (+1 d) EOT	6-8	9 (±1 d)	10- 13	14 (±1 d) EOS ^b
Study site visit	X			X ^c		X ^c		X ^c		X ^c
Informed consent form ^d	X									
RSV/influenza rapid diagnostic test ^e	X									
Inclusion/Exclusion criteria	X									
SARS-CoV-2 rapid diagnostic test ^f	X									
Demographics	X									
Medical history	X									
Smoking history	X									
Prior medications	X									
Vital sign measurements ^g	X					X				X
12-Lead ECG (resting)	X									
Physical examination ^h	X									
Weight, height, and BMI ⁱ	X									X
Pulse oximetry ^j	X					X				X
Frailty scale score (see SPM)	X									
Pregnancy test ^k	X (urine)	X (serum)								X (urine)
FSH ^l		X								
Clinical laboratory tests ^m		X				X				X
Randomization ⁿ		X								
eCOA Handheld eDiary ^o		X								X
RSV symptom diary eCOA ^p		X	X	X	X	X	X	X	X	X
		X	X	X	X	X	X	X	X	X
NP swab collection: confirmatory respiratory pathogen panel		X								
NP swab collection: RSV RNA quantitation of viral load		X		X		X		X		X
		X		X		X		X		X
RSV serology collection		X								X
		X								X
Study drug dosing ^s		X ^s	X	X	X	X ^s				
Study drug accountability ^t				X		X				X
PK sample collection		X ^u		X ^u		X ^u				X ^v
Concomitant medications ^w		X	X	X	X	X	X	X	X	X
Adverse events	X	X	X	X	X	X	X	X	X	X

Abbreviations: BMI = body mass index; COPD = chronic obstructive pulmonary disease; d = day; ECG = electrocardiogram; eCOA = electronic clinical outcome assessment; EOS = end-of-study; EOT = end-of-treatment; FSH = follicle-stimulating hormone; ICF = informed consent form; NP = nasopharyngeal; PK = pharmacokinetic; RSV = respiratory syncytial virus; SARS-CoV-2 = severe acute respiratory syndrome coronavirus 2; SPM = Study Procedures Manual. Note: Refer to the Laboratory Manual for sample collection and processing details.

- ^a Day 1 assessments to be performed in randomized subjects.
- ^b Subjects who discontinue treatment early (ie, prior to completing 5 days of dosing) or the study early (ie, prior to Day 14) should return to the study site within 24 hours and no more than 48 hours later to complete the EOS procedures.

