Unless otherwise specified, the baseline is defined as the last non-missing assessment value for a subject, for that particular parameter, that is prior to or on the date of first dose of study drug. For subjects who are randomized, but not treated, the baseline will be defined as the last non-missing assessment prior to or on the date of randomization. Percent change from baseline will be calculated as the [change divided by baseline] multiplied by 100. In the event change=0, then the percent change will be 0. In the event baseline=0, then the percent change will be missing.

The date of first dose and the date of last dose will be the date collected on the End of Treatment eCRF.

For the reporting of this study both CDISC SDTM (SDTM Implementation Guide version 3.2) and ADaM (ADaM Implementation Guide version 1.1) standards will be applied. A subject will

be considered to have completed the study after his/her attendance at the last planned study visit (Day 14 ± 1 day), or the last unscheduled visit (if any occur), as applicable. For each subject his or her study completion status (Yes/No) is recorded on the End of Study CRF.

Summary Tables and Figures will be presented by treatment group. Tables and Figures values for treatment group will be labelled as follows: • “EDP-938 800mg” • “Placebo”. Models will include stratification factor for asthma/COPD status unless an insufficient amount of data exists where convergence or the analysis cannot be performed.

[REDACTED]

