#### 3.14.1 Primary Efficacy Analyses

The primary efficacy analysis will be performed on the total symptom score (TSS) AUC on the respiratory syncytial virus symptom diary (see Appendix 5.2) using the mITT population. The primary efficacy analysis will be repeated using the PP population. The TSS is measured twice daily using a 13-point symptom scale. Date and time of completion will be recorded. For Day 1,

the TSS is measured first pre-dose and then post-dose. Subjects have been instructed to complete the symptom scale either immediately before or 4 hours after using acetaminophen medication to avoid confounding results. From Day 1 through Day 14, subjects will electronically record the date and time of any acetaminophen use.

The TSS will be derived for each subject using the electronic data capture handheld device (ERT® electronic clinical outcome assessment [eCOA] Handheld eDiary) or paper diary. Baseline TSS will be collected once on Day 1 prior to first dose. If baseline TSS is missing, the assessment of TSS post-dose on Day 1 will be used as baseline. The average daily TSS will be computed as part of the primary efficacy endpoint analysis.

The TSS will be derived for each subject, separately for each of the two assessments on each day (Day 1 to Day 14) as follows:

- 1) For each assessment, sum the 13 observed symptom grade values for a total symptom score. If any of the 13 observed values are missing the total symptom score will not be calculated for that assessment.

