The TSS AUC from Day 1 through Day 14 will be calculated using the trapezoid rule (*Matthews et al., 1990*). The AUC will require at least 2 non-missing calculated total symptom scores. Missing total symptom score data will be reviewed for potential impact, and any decisions to include subjects that fail these criteria above will be documented. The AUC will be calculated based on available individual assessments of TSS collected twice per day from Day 1 through Day 14, and the actual date/time of each assessment will be used for the calculation. For the baseline TSS, the actual time is set as 0. For each assessment post first dose, the actual time in days is computed as difference between the date/time of the assessment and the date/time of the first dose. The AUC is also standardized for 14 days by multiplying  $14/t_{last}$  where  $t_{last}$  is the actual time in days of the last available assessment. Additionally, the AUC from Day 1 through Day 3, the AUC from Day 1 through Day 5, and the AUC from Day 1 through Day 9 will be also derived and standardized similarly as for AUC from Day 1 through Day 14.

The AUC TSS from Day 1 through Day 14 will be compared between EDP-938 and placebo using an analysis of covariance (ANCOVA) model with treatment group, asthma/COPD status (present or absent) as factors and the baseline TSS as a covariate. The analysis will be performed using SAS procedure MIXED. Treatment groups will be compared using a type III sum-of-squares. The least-squares means, standard errors and two-sided 95% confidence intervals (CI) will be presented for individual groups and the difference between groups. The same ANCOVA analysis will be performed for the TSS AUC from Day 1 through Day 3, from Day 1 through Day 5 and from Day 1 through Day 9.

Descriptive statistics will be displayed for TSS and change from baseline by day and timepoint and also for average daily TSS by day and will include at a minimum the number of non-missing measurements, mean, standard deviation, median, minimum, maximum, and 95% CI for the mean.

Multiple line graphs of TSS will be produced:

- (1) Observed mean TSS  $\pm$  95% confidence interval by days 1-14 and timepoint for each treatment group
- (2) Observed mean TSS (average per day)  $\pm$  95% confidence interval by days 1-14 for each treatment group

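### When the pre-dose symptom score is missing, the SAP uses the Day 1 post-dose score as baseline in the primary model, against the protocol's pre-dose definition

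*SAP*

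**What the plan says.** **Baseline.** Protocol 11.6.1 starts the TSS series from "the last nonmissing measurement (Baseline) collected prior to dosing". SAP 3.14.1 also plans a pre-dose baseline, and the diary table in SAP 3.6 labels Day 1 timepoint 1 as pre-dose and timepoint 2 as post-dose. SAP 3.14.1 then adds: "If baseline TSS is missing, the assessment of TSS post-dose on Day 1 will be used as baseline". A TSS is not calculated if any of the 13 items is missing, so an incomplete pre-dose diary triggers the fallback as well as an absent one.

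**Use of baseline.** Baseline TSS is the covariate in the primary ANCOVA and the reference for change from baseline (SAP 3.14.1). It is also a covariate in the Cox model for time to resolution (SAP 3.14.1.1). For the AUC, "For the baseline TSS, the actual time is set as 0"; any assessment after the first dose takes its actual elapsed time.

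**Collection.** Protocol 7.1.2 states: "Eligible subjects must complete the Day 1 biological sample collections (ie, blood, urine, and nasopharyngeal swab[s]) prior to receiving the first dose". Protocol 8.4 repeats the list: "The Day 1 collection of blood, urine, and nasopharyngeal swab samples will be completed prior to administration of study drug". Neither names the diary. Protocol 8.3.8 schedules the diary "At Screening and at timepoints indicated in the SoA", but the Schedule of Assessments has no Screening tick for it. The Day 1 tick is in the eligible-subjects column, whose footnote reads "Day 1 assessments to be performed in randomized subjects"; neither that footnote nor the diary footnote says pre-dose.

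**General rule.** SAP 3.1 defines baseline, where nothing else is specified, as the last non-missing value "that is prior to or on the date of first dose of study drug". That is a rule by date, not by time.

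**The concern.** A score taken after randomisation and after the first dose can be affected by treatment. As a covariate, it lets the model adjust away part of any effect present by then. The comparison affected is the primary one, planned at 27 evaluable subjects per group and 80% power.

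Two further points follow. The substituted score meets both SAP timing rules, as a baseline and as a post-dose assessment, so two programmers could compute different AUCs from the same record. And how often the fallback is used depends on site workflow on Day 1, when consent, testing, randomisation, device issue and first dosing all occur and no binding instruction puts the diary before the dose.

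**Working it through.** **1. The plan's own figure.** Inputs from Protocol 11.2: means 500 and 225 (difference 275), SDs 450 and 200, unequal-variance t-test. Protocol 11.1 gives two-sided alpha 0.05. With Satterthwaite degrees of freedom and a noncentral t, power is 79.0% at 26 per group and 80.6% at 27, so 27 is reproduced. With 20% dropout, 27/0.8 = 33.75, or 34 per group, in line with the stated approximate 35. A pre-dose-only baseline changes none of this.

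**2. Attenuation through the covariate.** Let f be the share of subjects with a substituted baseline, rho the correlation of baseline TSS with TSS AUC, and d the Day 1 post-dose treatment difference in favour of the drug, in baseline-SD units. Substitution shifts the arm difference in the mean covariate by f × d. The slope of AUC on the standardised covariate is rho × SD_AUC. Hence

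attenuation ≈ f × rho × SD_AUC × d,

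with SD_AUC = sqrt((450² + 200²)/2) = sqrt(121,250) = 348.2.

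The documents give no f, rho or d; the values below are assumptions. Power is the formula of step 1 at 27 per group, with the difference reduced by the attenuation.

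| f | rho | d | Attenuation | Share of 275 | Power |
|---|---|---|---|---|---|
| 5% | 0.3 | 0.1 | 0.05 × 0.3 × 348.2 × 0.1 = 0.5 | 0.2% | 80.5% |
| 10% | 0.6 | 0.3 | 0.10 × 0.6 × 348.2 × 0.3 = 6.3 | 2.3% | 78.8% |
| 30% | 0.6 | 0.5 | 0.30 × 0.6 × 348.2 × 0.5 = 31.3 | 11.4% | 70.6% |

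Simulated ANCOVA (20,000 trials per case, 27 per group) agrees. In the second case the estimate is 268.1 with the fallback and 274.4 with the true baseline; in the third, 245.0 and 275.6. With d = 0, or with a strictly pre-dose baseline, this bias is zero.

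Protocol 11.2 states no units for the AUC, so the share of the planned difference is the safer column to read.

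**3. Time axis.** A substituted score could be placed at time 0 (baseline rule), at its actual time (post-dose rule), or at both. Suppose it is placed at its actual time, half a day after dosing, with an assumed TSS of 10 to 15. The AUC then omits about 0.5 × 10 = 5 to 0.5 × 15 = 7.5 score-days. The SAP factor 14/t_last does not restore this: with t_last = 14 it equals 1. Scaling by the observed interval gives 14/(14 − 0.5) = 1.037, which does allow for the missing half-day.

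**The case against.** The strongest reply is that a pre-dose diary is clearly intended, so the fallback should seldom be used. That stands. Protocol 8.3.8 and SAP 3.6 and 3.14.1 all point to a pre-dose entry, and the pre-dose list in Protocol 7.1.2 covers biological samples, where a questionnaire would not be expected. A reader might infer that the plan has no pre-dose diary; the documents do not support that. The gap is narrower: 8.3.8 and the Schedule of Assessments disagree, and no instruction holds the dose until the diary is entered.

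Other stronger readings also fail:

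- The mention in Protocol 11.6.1 of entries before or after treatment might be taken to permit a post-dose baseline. It describes the twice-daily entries over the study, and the same paragraph requires a pre-dose baseline.
- The bias might be called one-directional. Attenuation requires a Day 1 effect in favour of the drug. Protocol 1.5 reports headache as numerically more common on EDP-938 in Phase 2a, and headache is a TSS item, so the sign is not assured.
- The score might be said to be placed at time 0. Two SAP rules apply to it, so this is an ambiguity.
- The SAP 3.1 rule might be said to contaminate the FLU-PRO baseline. The FLU-PRO sections of the SAP are not visible, so this cannot be checked.

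The recall period also limits the size. SAP 5.2 asks for the last 12 hours at the Day 1 morning diary and the worst severity since the previous diary thereafter. A subject with no earlier entry would plausibly still report pre-dose symptoms, and only one dose has been taken.

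Finally, Protocol 11.1 allows non-principal analysis changes in the SAP before unblinding, with justification. The fallback is therefore not prohibited, but the visible SAP text gives no justification and no sensitivity analysis without the substituted values.

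**Conclusion.** The conflict holds. SAP 3.14.1 admits a post-dose score as baseline where Protocol 11.6.1 requires a pre-dose one, and that score enters the primary ANCOVA, change from baseline and the Cox model. Attenuation follows if the drug already relieves symptoms on Day 1.

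The size is probably small and cannot be computed from the documents. The range of 0.2% to 11.4% rests entirely on assumed f, rho and d; its upper end needs 30% of subjects substituted and a half-SD effect after one dose, neither of which the documents support. A reader might infer a material loss of power or a compromised primary result, and the evidence does not go that far. The ambiguity on the AUC time axis is real whatever the direction of effect. The point merits correction because it concerns the primary model and can be settled by wording before unblinding.

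**What to change.** 1. **Protocol 7.1.2 and Schedule of Assessments:** state that the first RSV symptom diary is completed before the first dose, and reconcile 8.3.8 with the schedule.
2. **SAP 3.14.1, covariate:** delete the post-dose substitution. If the pre-dose TSS is missing, fill the covariate only, with the pooled, arm-blind pre-dose mean within the asthma/COPD stratum, or overall if a stratum is sparse. Keep the post-dose rule at most as a sensitivity analysis.
3. **SAP 3.14.1, AUC:** for these subjects, keep the post-dose score at its actual time and standardise by 14/(t_last − t_first) instead of 14/t_last.
4. **SAP 3.1:** define baseline as before the date and time of first dose wherever times are recorded.

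The cost is a few minutes at the site before dosing, some wording, and a less informative covariate for the few subjects affected. The sample size is unchanged.

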### 3.14.1.1 Sensitivity Analysis of the Primary Endpoint

If acetaminophen use is within 4 hours before a TSS, then the TSS may have been impacted. Thus, TSS AUC for mITT analysis will be reproduced after excluding such TSS assessments post-baseline.

Time to resolution of TSS will be analyzed using a Cox Proportional Hazards model. This will be performed for the mITT population. Stratification factors, baseline TSS and asthma/COPD status (present or absent), will be included. Time to resolution of TSS will be defined as the time from first dose to first of two consecutive timepoints where TSS is zero (days). Consecutive timepoints is defined as two consecutive timepoints planned per protocol, e.g. Day 2 timepoint 2 and Day 3 Timepoint 1. A Kaplan-Meier curve will display the probability estimates with resolution. Descriptive statistics on the graph will include the median and 95% confidence interval at a minimum.

### 3.14.2 Secondary Efficacy Analyses

The RSV RNA viral load will be measured in nasopharyngeal swab samples by quantitative reverse transcription polymerase chain reaction (RT-qPCR) on Days 1, 3, 5, 9 and 14. Viral load values reported as TD (Target Detected, but below LLOQ) will be set to the average of LOD (limit of detection) and LLOQ (lower limit of quantification). Viral load values reported as TND (Target Not Detected, below LOD) will be set to zero. Viral load data will be transformed using a log10 scale before analyses. In case of zero value, the log transformed value will be also set as zero.

There will be two readings for both RSV A and RSV B, one from each of the two wells (i.e. A1, A2, B1, and B2). In case of any technical failure, no readings will be reported for the standard test, but a re-test will be done using a different aliquot from the same sample to produce valid results. PPD's unblinded statistician will then review the data and identify samples meeting discrepancy criteria for RSV A or RSV B. For these samples, a re-test will be performed using a different aliquot from the same sample. The discrepancy criteria for RSV A (same for RSV B) are defined as the following:

- Both A1 and A2 are numeric, and A1/A2 is  $>10$  or  $<1/10$  (i.e., one log difference);
- One of A1 and A2 is numeric, and the other one is TD or TND
- One of A1 and A2 is TD, and the other one is TND

For each sample, the final data will contain one or two sets of results.

The final RSV value (for A and B separately) for each sample will be the simple mean of the readings in original scale based on the following:

- Two readings from the only set if the final data have only one set of results.
- Two readings from the set without discrepancy if the final data have two sets of results and one set has discrepancy while the other set has no discrepancy
- Four readings from both sets if the final data have two sets of results and both sets have discrepancy
- Four readings from both sets if the final data have two sets of results and both sets have no discrepancy

Note: The readings reported as TND (target not detected) will be replaced by zero and those reported as TD (target detected) will be replaced by the average of LOD and LLOQ in the calculation of the RSV value.

The RSV type of each subject will be determined based on the final RSV value at baseline. If the baseline of RSV A is bigger, then the RSV type is A; otherwise, it is B. The analysis of the viral load will be based on the log scale of the RSV.

The RSV RNA viral load AUC will be derived similarly as described in *Section 3.14.1*. The AUC will be calculated based on all available assessments collected on Days 1/baseline, 3, 5, 9, and 14 and the actual date/time of each assessment will be used for the calculation. For the baseline viral load (Day 1), time is set as 0. For each assessment post first dose, the actual time in days is computed as difference between the date/time of the assessment and the date/time of the first dose. The AUC is also standardized to 14 days by multiplying  $14/t_{\text{last}}$  where  $t_{\text{last}}$  is the actual time in days of the last available assessment. Additionally, the AUC from Day 1 through Day 3, the AUC from Day 1 through Day 5, and the AUC from Day 1 through Day 9 will be also derived and standardized similarly as for AUC from Day 1 through Day 14.

An ANCOVA model with treatment group and asthma/COPD status (present or absent) as factors, and the baseline RSV RNA viral load as a covariate will be performed for the RSV RNA viral load AUC from Day 1 through Day 14. Treatment groups will be compared using a type III sum-of-squares. The least-squares means, standard errors and two-sided 95% confidence intervals (CI) will be presented for individual groups and the difference between groups. The same ANCOVA analysis will be performed for the AUC from Day 1 through Day 3, from Day 1 through Day 5, and from Day 1 through Day 9.

The proportion of subjects with RSV RNA viral load below the limit of detection (LOD) will be analyzed on Days 1, 3, 5, 9, and 14, respectively. Treatment groups will be compared at each visit day using a Cochran-Mantel-Haenszel test controlling for the stratification factors of asthma/COPD status (present or absent). Additionally, the number and proportion of subjects with RSV RNA viral load below LOD will be summarized for each treatment group, and their respective 95% CIs will be reported based on the normal approximation. The adjusted difference in proportions between the 2 treatment groups will be computed as a weighted average of the treatment differences across strata using the Mantel-Haenszel weights, and the associated 95% CI will be provided using the Sato variance estimator (Sato, 1989).

[figure not shown]
Time to RSV RNA viral load below LOD will be analyzed using a Cox Proportional Hazards model. Stratification factors, baseline RSV RNA viral load and asthma/COPD status (present or absent), will be included. For calculating time to RSV viral load below LOD it is required of at

least two consecutive timepoints (or end of study) with viral load below LOD. Time to RSV viral load below LOD will be defined as the time between the date of first dose to the first date of achieving viral load below LOD, of the two consecutive timepoints or end of study. Subjects who discontinue early and subject who do not achieve viral load below LOD will be censored at the end of study date reported on the End of Study CRF. A Kaplan-Meier curve will display the probability estimates of achieving RSV RNA viral load below LOD. Descriptive statistics on the graph will include the median and 95% confidence interval at a minimum.

Descriptive statistics will be displayed for RSV RNA viral load and change from baseline by visit (Days 1, 3, 5, 9 and 14) and will include at a minimum the number of non-missing measurements, mean, standard deviation, median, minimum, 25th percentile, 75th percentile, maximum, and 95% CI for the mean.

Line graph of RSV RNA viral load will be produced:

- (1) Observed mean viral load  $\pm$  95% confidence interval by days (1, 3, 5, 9 and 14) for each treatment group

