11. STATISTICAL CONSIDERATIONS

11.1 General Considerations

Statistical analysis of this study will be the responsibility of Enanta Pharmaceuticals, Inc. or its designee. Details of the statistical analysis methods will be described in the statistical analysis plan (SAP) document.

Continuous endpoints will be summarized using n, mean, standard deviation, median, 25th quartile, 75th quartile, minimum, and maximum values. Categorical endpoints will be summarized by the number of subjects meeting the endpoint and the percentage of subjects out of the appropriate population. The denominator will be displayed when needed. Statistical inference will be performed as appropriate. Inferential testing will be conducted using a two-sided alpha of 0.05, unless stated otherwise.

Any change to the data analysis methods described in the protocol will require an amendment if it changes a principal feature of the protocol. Any other change to the data analysis methods described in the protocol, and the justification for making the change, will be described in the clinical study report or SAP. Changes may only be made in the SAP prior to unblinding.

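### Undetected RSV RNA is scored as log10 = 0 (1 reporting unit), so the size of the viral load AUC difference and of the mean change from baseline depends on the unit

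*SAP*

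**What the plan says.** SAP 3.14.2 has two rules for samples below the LLOQ. A sample that is detected but not quantifiable (TD) takes the midpoint of LOD and LLOQ. For an undetected sample (TND), "Viral load values reported as TND (Target Not Detected, below LOD) will be set to zero". On transformation, "In case of zero value, the log transformed value will be also set as zero".

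These values go into every numerical viral load summary: "The analysis of the viral load will be based on the log scale of the RSV". For the AUC, "The AUC will be calculated based on all available assessments collected on Days 1/baseline, 3, 5, 9, and 14", using the trapezoid rule. "The AUC is also standardized to 14 days by multiplying" 14 over the time of the last available assessment. The AUC is compared by ANCOVA with least-squares means and 95% confidence intervals. Change from baseline is described by visit, and mean viral load is plotted.

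The proportion below LOD and the time to below LOD are analysed separately. They use detection status, not the value given to TND. Neither document states the LOD, the LLOQ or the reporting unit; Protocol 8.5.3 refers to the Laboratory Manual for further details. No planned analysis varies the value given to TND.

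**The concern.** A TND result says only that the load is below the LOD. Scoring it as log10 = 0 places it at exactly 1 unit, a point fixed by the choice of unit and not by the assay. Expressed in a unit one tenth the size, the same samples would all gain 1 log10 if detected and nothing if not.

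Viral load AUC is the first-listed secondary endpoint, and Protocol 4.2.1 names it as the measure of antiviral efficacy. Its least-squares mean difference will be read as an amount of log10 reduction over time. If that amount changes with the unit, it has no fixed meaning. TND samples are expected in number, since the SAP plans analyses below LOD on Days 3, 5, 9 and 14.

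**Working it through.** **Plan's own figures.** There is none for viral load. The only sizing figure is for TSS AUC (Protocol 11.2): means 500 and 225, SDs 450 and 200. At two-sided 0.05, the unequal-variance t-test has 80.6% power with 27 per arm. Dropout gives 27/0.8 = 33.75, so 34 per arm and 68 in total, against about 35 and 70. This reproduces and is not affected by the present point.

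**Step 1: the gap in the scale.** Under the SAP's averaging of replicate readings, the smallest non-zero final value arises when half the readings are TD and half TND: half of (LOD + LLOQ)/2, that is (LOD + LLOQ)/4. Since LLOQ is at least LOD, this is at least LOD/2. With an assumed LOD of 100 units (2.0 log10), no final value can lie between 0 and log10(50) = 1.70. In a unit where (LOD + LLOQ)/4 is below 1, such a detected sample would have a negative log and rank below an undetected one.

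**Step 2: AUC weights.** Days 1, 3, 5, 9 and 14 are nominally t = 0, 2, 4, 8 and 13 days. The trapezoid weights are 1, 2, 3, 4.5 and 2.5. Multiplied by 14/13, they become w = 1.08, 2.15, 3.23, 4.85 and 2.69.

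**Step 3: effect of the unit.** Let pA and pP be the TND shares on EDP-938 and placebo at each visit, and D = sum of w x (pA - pP). Changing the unit so that detected log10 values rise by k changes the AUC difference by k x sum of w x [(1 - pA) - (1 - pP)] = -k x D. Under an LOD-tied value, every sample in both arms rises by k and the difference does not change. This step needs no assumption about the assay.

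**Step 4: effect of the substituted value.** Replacing a TND value of c (log10) by 0 changes the difference by -c x D. It enlarges a difference in favour of EDP-938 only if c is above 0 (substituted value above 1 unit) and D is above 0 (TND more frequent on EDP-938).

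**Step 5: assumed numbers.** Assumed true log10 means at the five visits were 6.5/4.6/3.2/1.2/-0.5 on EDP-938 and 6.5/5.2/4.1/2.0/0.0 on placebo, with assumed SDs and 200,000 simulated subjects per arm. The true difference follows from the means: 2.15 x 0.6 + 3.23 x 0.9 + 4.85 x 0.8 + 2.69 x 0.5 = 9.4 log10-days in favour of EDP-938.

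| Assumed LOD (log10) | TND log10 = 0 (SAP) | TND = LOD/2 | TND = LOD | True, simulated |
|---|---|---|---|---|
| 1.0 | -8.3 | -7.4 | -6.9 | -9.5 |
| 2.0 | -8.6 | -5.9 | -5.4 | -9.5 |
| 3.0 | -8.4 | -4.2 | -3.8 | -9.4 |

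At LOD 2.0 the SAP rule gives -7.0, -8.6, -10.2 and -13.3 for k = -1, 0, 1 and 3. That is a steady change of about 1.59 per log10 of unit, so D = 1.59. The gap between the SAP rule and substitution at the LOD agrees: 8.59 - 5.41 = 3.18 = 2 x 1.59.

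**Step 6: change from baseline.** At Day 9 and LOD 2.0 the simulated TND shares were 0.70 and 0.50, with none at baseline. Each log10 of unit therefore moves the mean change by -0.70 on EDP-938 and -0.50 on placebo, and their difference by -0.20. The Day 9 difference is -0.73 under the SAP rule and -0.32 with TND = LOD; the gap of 0.41 matches 2 x 0.20 within rounding.

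**Step 7: the test.** At LOD 2.0 the SD of the AUC rises with the estimate (14.0 against 9.2 with TND = LOD). The standardised effect is 0.615 against 0.592, and approximate power at 35 per arm is 73% against 70%. The gap is about 1 point at LOD 1.0 (75.1% and 74.2%) and 8 points at LOD 3.0 (68.2% and 60.2%). With equal arms the simulated difference is about 0 under every rule.

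**Step 8: a second scenario.** Assume a baseline of 6 log10 and declines of 0.42 and 0.55 log10 per day. The true difference is -0.13 x (2.15 x 2 + 3.23 x 4 + 4.85 x 8 + 2.69 x 13) = -11.8. With assumed SDs and LOD 2.0, the SAP rule gives -9.2, and -7.3 or -11.0 when the unit changes tenfold either way. Substituting LOD/2 gave -4 to -8 across the assumptions tried. A left-censored analysis gave about -12.2 against a simulated truth of -11.9.

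**The case against.** The strongest defence is that the rule is prespecified, applies identically to both arms and is reproducible once the laboratory's unit is fixed. It affects a secondary Phase 2b endpoint and leaves the test result much as it was. Change from baseline is only described, and its medians and quartiles are less sensitive to the substituted value than the mean. All of this stands, and it limits the consequence. It does not remove the unit dependence, which follows from the text alone.

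A reader might infer that the rule overstates the antiviral effect. The documents do not support that. They give no LOD or unit, and a comparison with LOD/2 is not a comparison with the truth. In both scenarios above the SAP rule, in the base unit, fell short of the true difference, and LOD/2 fell further short. In another unit it can exceed the truth: -10.2 against -9.5 in Step 5. Nor is it established that 1 unit lies far below what the assay can measure; that needs an LOD well above 1 unit.

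A reader might also infer that clearance is counted twice. It is not: AUC, proportion below LOD and time to below LOD are reported separately, and any substitution makes the AUC partly reflect clearance.

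Finally, LOD/2 is itself a convention. Making it the main rule would be a trade-off, not a correction.

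**Conclusion.** The point holds in a limited form. Under SAP 3.14.2 the size of the viral load AUC difference and of the mean change from baseline depends on the reporting unit whenever the TND shares differ between arms, so neither can be read as a measured log10 reduction. The dependence is exact: D log10-days per log10 of unit, about 1.6 in the first scenario at LOD 2.0. The value of D and every other magnitude rest on assumed means, SDs and LOD.

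The direction of error against the true load is unknown. Relative to LOD-tied substitution, the rule enlarges the difference only under the two conditions in Step 4. It has no effect when the weighted TND shares are equal and works the other way if TND is more frequent on placebo. It manufactures no effect between equal arms, and power changes far less than the estimate does. A left-censored analysis is a cheap and better-founded addition; replacing the main rule is not required.

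**What to change.** Before unblinding, add to SAP 3.14.2:

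1. A left-censored (Tobit-type) repeated-measures analysis of log10 viral load, with samples below the LOD entered as censored at the LOD. Derive the AUC difference from the visit means with the weights above, and report it beside the planned ANCOVA.
2. A repeat of the AUC ANCOVA with TND set to an LOD-tied value (for example LOD/2 or LOD) as a sensitivity analysis.
3. A statement of the reporting unit, LOD and LLOQ with the results.

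Classification as below LOD, and the two endpoints built on it, stay as they are.

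The cost is a little extra programming and one more estimate to explain, since the methods may give AUC differences of different size. The censored model also relies on normality below the LOD. That reliance is heaviest at late visits: in the first scenario at LOD 2.0, 95% and 91% of Day 14 samples were undetected.
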